5.1 Definition of Dose Limiting Toxicity (DLT)

DLTs will be defined by toxicity occurring during the first 5 weeks of this study. A DLT will be any non-pulmonary AE of Grade 3 or higher that is at least possibly treatment-related with the exception of nausea and vomiting which have not been treated with optimal anti-emetic therapy. Any DLT that causes a patient to miss > 28 consecutive days of simvastatin will result in the patient being taken off treatment.

A DLT is defined as a toxicity considered at least possibly related to simvastatin. In this regard, it is important to consider the possibility that co-administration of simvastatin may increase the toxicity of sirolimus or everolimus. Conversely, sirolimus or everolimus might influence the toxicity profile of simvastatin. Thus, it may be difficult to confidently attribute certain observed toxicities solely to either simvastatin and sirolimus, or simvastatin and everolimus. With this potential complication in mind, an attempt will be made to define dose-limiting toxicities (DLTs), which apply specifically to simvastatin. In this study, DLTs will include any possibly, probably, or definitely simvastatin-related Grade 3 or 4 toxicity. Known toxicities specific to sirolimus and everolimus such as mucositis will not be considered dose limiting unless the treating physician considers the toxicity to be exacerbated by simvastatin. Toxicities that will be attributable to simvastatin include but are not limited to abdominal pain, nausea, diarrhea, headache, and infectious complications.

The target DLT rate is $\leq 33\%$. The maximum tolerated dose (MTD) will be defined as a) the dose producing DLT in 2 out of 6 patients, or b) the dose level below the dose which produced DLT in ≥ 2 out of 3 patients, or in ≥ 3 out of 6 patients. Patients will be evaluable for a DLT if they have finished 5 weeks of combined therapies. Patients who are removed from study due to clinical progression prior to the 5 week period will be replaced. Patients will be evaluable for response if they have completed 90% of their expected dose of simvastatin for the 8 weeks. Patients will be evaluated for toxicity if they received at least one dose of simvastatin.

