5.2.2 Dose Delays

For patients who are unable to tolerate the protocol-specified dosing schedule, dose adjustments are permitted in order to keep the patient on study drug. If administration of sirolimus or everolimus must be interrupted because of unacceptable toxicity, drug dosing will be interrupted or modified according to rules described in Section 6.4. Major Events are non-treatment-related grade 3 and 4 pulmonary and non-pulmonary toxicities. Treatment should be delayed for major events if simvastatin may further complicate the non-treatment related event. If a major event requires a delay of treatment, treatment must be delayed until toxicity is resolved (\leq Grade 1 or \leq Baseline). For treatment-related toxicities and major events, if toxicity is not resolved in \leq 4 weeks, patient will be taken off the treatment that is most likely to be related to the toxicity. While this most likely will result in coming off study, at the investigator's discretion patients may continue on single agent therapy, if toxicities are \leq grade 2 and there is some evidence of clinical benefit to the patient.

Table 2A: Approach to overlapping toxicities of simvastatin and sirolimus*

Overlapping Toxicity	Dose Reduce First	Dose Reduce Second
Mucositis	sirolimus	simvastatin
Nausea	sirolimus	simvastatin
Abdominal pain	simvastatin	sirolimus
Infections	sirolimus	simvastatin
Diarrhea	sirolimus	simvastatin
Headache	simvastatin	sirolimus

Table 2B: Approach to overlapping toxicities of simvastatin and everolimus*

Overlapping Toxicity	Dose Reduce First	Dose Reduce Second
Mucositis	everolimus	simvastatin
Nausea	everolimus	simvastatin
Abdominal pain	simvastatin	everolimus
Infections	everolimus	simvastatin
Diarrhea	everolimus	simvastatin
Headache	simvastatin	everolimus

*At the discretion of the treating physician.

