5.2.3 Simvastatin Dose Reduction

Any AE of \geq Grade 3 and attributed as possibly, probably or definitely related to simvastatin will result in the dose being held until the AE has resolved to \leq grade 1 or baseline, while sirolimus dosing may continue uninterrupted. If the AE resolves, reinstatement of treatment can occur but at a reduced dose as described in Table 3. If the AE recurs at the reduced dose, treatment will be held until the AE has resolved to \leq grade 1 and when resolved treatment can be reinstated at the next lower dose level. No more than 2 dose reductions are allowed during the maintenance cycles.

Table 3: Simvastatin Dose Reduction Schema

Dose mg/day	Reduce to
20 mg daily	15 mg daily
15 mg daily	10 mg daily
40 mg daily	30 mg daily
30 mg daily	20 mg daily

Toxicities that may be attributable to simvastatin include nausea, abdominal pain, diarrhea, upper respiratory infections, headache, and diarrhea. If any of these AEs occur at grade \leq 2, simvastatin may be continued and the AE managed with supportive care. For any AE with a grade \geq 3, the rules outlined in Sections 5.3 apply for holding of dose, dose reduction, removal from study and reporting requirements.

The main laboratory abnormalities which may result from simvastatin include increased CPK and liver transaminases. Patients who develop increased CPK levels ($> 2X$ ULN) will be followed with weekly CPK levels until the abnormalities return to normal. Simvastatin will be continued if CPK values are decreasing on the following week's blood sample. If persistent elevations ($> 2X$ ULN) occur over two weeks (three assessments), or symptoms such as muscle pain are present, the simvastatin study drug will be stopped. The simvastatin study drug will be stopped immediately if myositis (CPK $> 10 \times$ ULN) is documented at any time.

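### Section 5.1 makes finishing the 5-week DLT window the only stated route to DLT evaluability, so a patient stopped early because of a DLT can fall out of the DLT rate

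*Combined protocol and SAP*

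**What the plan says.** Section 5.1 sets the observation window: "DLTs will be defined by toxicity occurring during the first 5 weeks of this study". Later in the same section it sets the evaluability rule: "Patients will be evaluable for a DLT if they have finished 5 weeks of combined therapies". The next sentence covers early leavers, but for one reason only: "Patients who are removed from study due to clinical progression prior to the 5 week period will be replaced". The section also gives a target DLT rate of 33% or less.

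Several rules allow a DLT to interrupt or end simvastatin:

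- Section 5.1: "Any DLT that causes a patient to miss > 28 consecutive days of simvastatin will result in the patient being taken off treatment".
- Section 5.2.2: if toxicity has not resolved within 4 weeks, the "patient will be taken off the treatment that is most likely to be related to the toxicity".
- Section 5.2.3: an event of grade 3 or above "attributed as possibly, probably or definitely related to simvastatin will result in the dose being held until the AE has resolved to" grade 1 or baseline, with restart possible at a reduced dose.
- Section 5.2.3: "The simvastatin study drug will be stopped immediately if myositis" is documented, given there as CPK above 10 times the upper limit of normal. No restart is described.
- Section 9.2: a serious event leads to discontinuation until the DSMB has reviewed the case.

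Other text suggests a wider set. Section 5.1 itself ends with "Patients will be evaluated for toxicity if they received at least one dose of simvastatin", and sections 9.2 and 11.2 say the same for safety. The protocol summary and sections 6.1, 7.1 and 10.12 refer to intention to treat, and 7.1 keeps data acquired before termination in the primary analysis. Section 11.1 bases the DLT intervals in Table 5 on 9 patients evaluable over 120 days.

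**The concern.** The condition for being counted and the period in which the event is counted are the same 5 weeks, and the event can itself stop a patient from meeting the condition. When such a patient is left out, the numerator and the denominator each lose one, which lowers the observed rate.

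The DLT rate is the safety quantity to which the protocol attaches a numerical target and for which section 11.1 tabulates exact intervals, in a study whose primary objective is safety. If the set is left open, it will be chosen after the events are known. With at most 10 patients, moving one or two of them can put the estimate on the other side of 33%.

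**Working it through.** **The plan's own figures.** Section 11.1 takes 10 × (1 − 0.10) = 9 patients. The probability of seeing no DLT is (1 − p)^9. At the rounded rates this gives 0.89^9 = 35.0%, 0.78^9 = 10.7%, 0.67^9 = 2.7%, 0.56^9 = 0.5% and 0.44^9 = 0.06%, which reproduces the probability row of Table 5. The exact 95% interval for 3/9 is 7.5% to 70.1%, which matches the printed entry.

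**Who is dropped on a literal reading.**

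- *Permanent stop for a DLT before week 5:* she has not finished 5 weeks of combined therapy and no other route is stated, so she is out. The CPK stop in 5.2.3 is an example if the event is graded 3 or higher and judged at least possibly related.
- *Hold with restart:* unclear. It depends on whether held days count towards the 5 weeks.
- *Hold leading to removal:* a hold of 28 days that starts on day 7 runs to day 35. Removal under the 28-day or 4-week rules therefore falls inside the window only if the hold began by about day 7.

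**Effect on the rate.** Let p be the true DLT rate, q the share of DLT patients who do not finish 5 weeks, and r the share of other patients who do not finish. The documents give neither q nor r, so both are assumptions. The expected rate among finishers is

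p(1 − q) / [p(1 − q) + (1 − p)(1 − r)].

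For p = 1/3, with r = 10% borrowed from the 120-day attrition figure:

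| q | r = 0 | r = 10% |
|---|---|---|
| 0 | 33.3% | 35.7% |
| 10% | 31.0% | 33.3% |
| 25% | 27.3% | 29.4% |
| 50% | 20.0% | 21.7% |
| 75% | 11.1% | 12.2% |
| 100% | 0% | 0% |

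Worked entry (q = 0.25, r = 0): (1/3 × 0.75) / (1/3 × 0.75 + 2/3) = 0.250 / 0.917 = 27.3%.

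The direction depends on q against r. Equal losses (10% and 10%) give no bias, and losses only among patients without a DLT bias the rate upward. A true 40% with q = 0.25 and r = 0 gives 0.30 / 0.90 = 33.3%, which is at the target.

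**Count example.** Take 10 treated and 4 DLTs, with k of the 4 not finishing. The reported rate is (4 − k)/(10 − k):

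- k = 0: 4/10 = 40% (exact 95% CI 12% to 74%)
- k = 1: 3/9 = 33%
- k = 2: 2/8 = 25% (exact 95% CI 3% to 65%)

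The intervals overlap widely. What changes is the side of the target on which the estimate falls.

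**The case against.** The best defence is that the sentence says *if*, not *only if*. A DLT is a kind of toxicity, and the same section evaluates toxicity in everyone with one dose. The intention-to-treat statements make inclusion at least as natural a reading. This stands in part: the text is ambiguous, and a reader who infers that the plan has a rule expelling DLT patients goes further than the wording. But none of those statements names the DLT denominator, and section 5.1 sets out DLT evaluability, response evaluability and toxicity evaluation as three separate sentences.

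A reader might also infer that the hold and stop rules make understatement likely. The documents do not support that. Section 5.2.2 permits dose adjustments so that patients can stay on study drug, and 5.2.3 allows restart at a reduced dose. The first scheduled laboratory tests after dosing are at day 30 ± 7, that is days 23 to 37, so a stop found on schedule comes close to the end of the window or after it. Earlier detection relies on the patient contacting staff. The route is narrow but not closed. The section 7.2 suspension could also interrupt patients without a DLT, which works in the other direction.

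A fatal event is not a clean example of a lost DLT. Section 5.1 defines DLT once as grade 3 or higher and once as grade 3 or 4, so whether a death counts is itself unsettled, and any death triggers the 7.2 suspension and DSMB review.

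Finally, little depends on the rate. It is not a listed endpoint, section 11.2 does not mention it, and results are descriptive. Section 9.2 requires a participation summary for each patient, so every event should remain visible. This stands, and it limits the severity. The MTD counts in 5.1 would inherit the same denominator, but the protocol describes no cohorts of 3 or 6, and escalation is decided patient by patient at visit 4, after the window has closed.

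**Conclusion.** The gap is real and minor. The only stated DLT-evaluability criterion is completion of the window in which DLTs are counted, no passage adds a route for a patient who had a DLT, and the treatment of held days is not stated. The one-dose and intention-to-treat passages must be reconciled with it.

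The observed DLT rate can be understated, on the condition that DLT patients fail to finish more often than others (q above r). The size cannot be fixed from the documents: a true 33.3% falls by about 2 points at q = 10%, 6 points at q = 25% and 13 points at q = 50%, all with r = 0. The larger distortions in the table need most DLT patients to be lost, and nothing in the protocol shows that this would happen.

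The 9 patients in section 11.1 could be taken as a third analysis population. That reads too much into it: 9 is a planning count. With all 10 evaluable, the three-DLT row would move only from 3/9 = 33% (7% to 70%) to 3/10 = 30% (7% to 65%).

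**What to change.** Replace the evaluability sentence in section 5.1 with: *Patients are evaluable for DLT if they received at least one dose of simvastatin and either had a DLT within the 5-week window or completed that window.* State whether days on hold count towards completion. Use this one set for the observed DLT rate and its exact confidence interval. Report the rate among all treated patients as a supplementary row.

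The supplementary row is needed because the new set leans slightly upward if patients without a DLT leave early. With p = 1/3 and 10% of them lost, the expected rate is (1/3) / (1/3 + 2/3 × 0.9) = 35.7%.

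Relabelling or recalculating the Table 5 denominator in section 11.1 to match is optional.

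The cost is a short edit to 5.1 and one extra table row. It needs no new data or visits and changes no dosing, hold or stopping rule. The downside is that the reported DLT rate may look less favourable.

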- Severe or uncontrolled medical conditions which would cause an unacceptable safety risk or compromise compliance with the protocol.
- Unstable seizures (recent changes in pattern or anti-epileptics).
- Mental illness or cognitive deficit precluding informed consent..
- Inability to attend scheduled clinic visits or comply with study procedures.

PRIMARY ENDPOINTS:

- Safety of simvastatin in the treatment of LAM-S or LAM-TS patients on a stable (for at least 3 months) dose of sirolimus or everolimus.

SECONDARY ENDPOINTS:

- Effect of simvastatin on forced expiratory volume in 1 second (FEV1) at days 0, 60, and 120.
- Effect of simvastatin on forced vital capacity (FVC) at screening and at days 0, 60, and 120.
- Effect of simvastatin on diffusing lung capacity (DLCO) at screening and at days 0, 60, and 120.
- Effect of simvastatin on VEGF-D serum levels at days 0, 30, 60, 90, and 120.
- Signs of clinical benefit.

STUDY OBSERVATIONS:

- Patients will be evaluated in person at baseline and at each study visit day.
- Chest x-rays will be obtained at screening and day 120.
- Laboratory tests including a complete blood count, routine chemistry tests (creatinine and transaminases) and lipid panel will be performed at screening and at days 30, 60, 90, and 120.
- Blood work for VEGF-D will be performed at days 0, 30, 60, 90 and 120 and for sirolimus or everolimus blood levels at screening and days 30, 60, 90 and 120.
- Patients will have spirometry (FEV1, FVC, and DLCO) performed at days 0, 60, and day 120.

SAMPLE SIZE AND POWER:

A total of up to 10 evaluable patients will be enrolled. As this is a safety study with a small number of patients, data will be compiled in descriptive tables of results.

DATA ANALYSIS:

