1.1 Background and Significance

Pulmonary lymphangiomyomatosis (LAM) is a slowly progressive neoplasm that targets the lung, causing cystic destruction and respiratory failure over one to two decades (*1*). LAM occurs in about 3.4–7.8 per million women (although it is likely to be substantially underdiagnosed) and in at least 30% of women with tuberous sclerosis complex. Clinically significant LAM occurs almost exclusively in women, although radiographic evidence of cystic lung disease consistent with LAM and a few biopsy-documented cases of LAM have been reported in men with and without TSC. The average age at diagnosis is about 35 years, typically delayed by 3–5 years due to confusion with more common causes of dyspnea, including asthma or chronic obstructive lung disease (*1*).

Up to 93% of patients with TSC and 32% of patients with LAM develop renal tumors called kidney angiomyolipomas (AML) (*1*). These tumors cause significant morbidity and mortality, and effective systemic treatment is not currently available. Both TSC and LAM are known to be caused by mutations in either of two tumor suppressor genes *tuberous sclerosis complex 1 (TSC1)*, encoding hamartin protein, or *TSC2*, encoding protein tuberin. When either *TSC1* or *TSC2* gene contain inactivating mutations, tuberin or hamartin produced by the gene is defective or deficient, protein function is lost, inducing the constitutive activation of mTOR signaling pathway that deregulates cell growth and survival (*1*). Figure 1 illustrates the deregulated TSC1/TSC2 signaling and its potential therapeutic targeting in LAM and TSC patients. Growth of LAM cell lesions in the lung and AML in kidney is partially suppressed by treatment with the FDA-approved drugs Everolimus or Sirolimus targeting the mTOR signaling pathway. Cessation of therapy results in tumor regrowth. While this therapy intervenes with tumor growth, none adequately addresses the tumor cell survival.

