7.1 Criteria for Terminating Participation on Study

An intent-to-treat approach will be used in this study. All data acquired prior to patient termination for the following reasons will be included in the primary analysis.

- Withdrawal of patient consent
- Withdrawal by the patient
- Withdrawal by the investigator
- Intercurrent illness or event that precludes further administration of treatment or ability to evaluate lung function (e.g. -mental status change, large pleural effusion).
- Pregnancy or failure to comply with adequate contraception
- Continuing patient non-compliance

Every effort will be made to conduct a final study visit and patients will be followed clinically until all study-related adverse events resolve, the patient's condition stabilizes or the adverse events are determined to be permanently ongoing.

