10.12 Patient withdrawal

A patient has the right to withdraw from the study entirely, at any time, for any reason, without prejudice to future medical care by the investigator or other physicians. The investigator also has the right to withdraw patients from the study in the event of concurrent illness, AEs, or other reasons deemed to be in the patient's best interest.

A patient should be withdrawn from the study if there is:

- Withdrawal of consent
- Termination of the study by the funding agency

In order to preserve the integrity of the intention-to-treat analysis, even if the patient is withdrawn from the treatment portion of the protocol (either due to patient, physician, or investigator decision), it is imperative to continue with the scheduled follow-up assessments, both for the safety of the patient and for completeness of data collection. This will be explained to potential patients at the time of informed consent. The importance of compliance with study visits will be reinforced throughout the study. If the treatment is permanently withdrawn, the patient will return to the LAM clinic for safety assessment (history, physical examination, and clinical laboratories, if necessary).

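### Section 5.1 replaces patients who progress before 5 weeks and its 90%-dose rule makes them non-evaluable for response, so they can fall out of the lung-function and clinical-benefit summaries

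*Combined protocol and SAP*

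**What the plan says.** Section 5.1 sets three evaluability rules and one replacement rule:

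- DLT: "Patients will be evaluable for a DLT if they have finished 5 weeks of combined therapies".
- Replacement: "Patients who are removed from study due to clinical progression prior to the 5 week period will be replaced". This is the only explicit replacement rule in the protocol.
- Response: "Patients will be evaluable for response if they have completed 90% of their expected dose of simvastatin for the 8 weeks".
- Toxicity: "Patients will be evaluated for toxicity if they received at least one dose of simvastatin".

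The Study Observations part of the protocol summary fixes the lung-function schedule: "Patients will have spirometry (FEV1, FVC, and DLCO) performed at days 0, 60, and day 120". Table 1 in section 4.2 agrees. VEGF-D, SGRQ and FPI are also collected at day 30.

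The protocol summary promises an intention-to-treat analysis. Section 7.1 adds: "All data acquired prior to patient termination for the following reasons will be included in the primary analysis". Its list of reasons includes withdrawal by the investigator but does not name clinical progression. It promises an attempt at a final visit without listing the procedures. Sections 6.1 and 10.12 ask that patients withdrawn from the treatment part keep to their scheduled assessments. For permanent withdrawal of treatment, section 10.12 says that "the patient will return to the LAM clinic for safety assessment (history, physical examination, and clinical laboratories, if necessary"; spirometry is not named.

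Clinical progression, response and clinical benefit are not defined. Nothing states how a replaced patient enters the FEV1, FVC, DLCO or clinical-benefit tables.

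**The concern.** Replacement here is triggered by a bad outcome, in an open-label study where the investigator judges progression without a stated definition. Section 1.1 describes LAM as a disease that "is a slowly progressive neoplasm that targets the lung, causing cystic destruction and respiratory failure over one to two decades", and section 1.2 says that rapamycin-based therapy stabilises lung function. Worsening within 5 weeks of adding simvastatin therefore deserves to be seen in the results.

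If such patients are swapped out and also fail the response rule, the secondary summaries describe only those who got through the first 5 weeks without progressing. Section 1.3.1 says a multi-center Phase II is planned once safety is established, and one secondary objective is a preliminary look at effectiveness and clinical benefit. In a single arm of about 10 patients, one or two such replacements would visibly move the summaries.

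**Working it through.** **The plan's own figure.** Section 11.1 expects 10 × (1 − 0.10) = 9 evaluable patients, which reproduces. It treats attrition as generic and does not say how a replaced patient is counted.

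**Spirometry.** Visit 3 is 30 ± 7 days after Visit 2 (section 4.3.3), and Visit 4 is 30 ± 7 days after Visit 3 (section 4.3.4).
- Earliest Visit 4 = 23 + 23 = day 46. Under the ± 7 days around day 60 in the section title, it is day 53.
- Five weeks = day 35, which is before either. A patient who leaves the study by then has only the day 0 test on schedule.
- Visit 3 spans days 23 to 37, so one post-dose set of VEGF-D, SGRQ and FPI may exist.

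**Dose share.** Eight weeks = 56 daily doses, and 90% is 0.9 × 56 = 50.4 doses. By day 35 she has taken at most 35, so her share is at most 35/56 = 62.5%. If Visit 4 and its dose increase fall before day 56, the expected total rises and her share falls, so 62.5% is a ceiling. This reads expected dose as the full 8-week amount, not the amount due up to removal.

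**Illustration of size.** The documents give no progression rate or effect size, so these inputs are assumptions: 10 patients retained, k replaced, and progressors' mean FEV1 change worse than the others' by D.
- Early progression: 0/10 in the retained set against k/(10 + k) in all dosed.
- Benefit proportion: r/10 against r/(10 + k), counting removed patients as no benefit.
- Mean FEV1 change looks better by D × k/(10 + k).

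| | k = 1 | k = 2 |
|---|---|---|
| Retained set (exact 95% CI) | 0/10 (0–31%) | 0/10 (0–31%) |
| All dosed (exact 95% CI) | 1/11 = 9.1% (0.2–41%) | 2/12 = 16.7% (2–48%) |
| Benefit shown as 3/10 = 30% | 3/11 = 27.3% | 3/12 = 25.0% |
| Benefit shown as 5/10 = 50% | 5/11 = 45.5% | 5/12 = 41.7% |
| FEV1 shift, D = 100–300 mL | 9–27 mL | 17–50 mL |

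Section 7.2 caps enrolment at ten patients, while sections 3.4 and 11.1 count ten evaluable. If the cap is ten enrolled, one replacement shows 0/9 instead of 1/10, and the FEV1 shift is 10% of D.

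**How often it would arise.** P(at least one in 10) = 1 − (1 − p)^10. For assumed early-progression risks p of 2%, 5%, 10% and 20%, this is 18%, 40%, 65% and 89%.

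**The case against.** The strongest reply is that the protocol elsewhere wants these data kept. Sections 6.1 and 10.12 press for continued scheduled assessments whoever decides on withdrawal, and the investigator-withdrawal item in 7.1 plausibly covers a patient removed for progression. If those provisions are applied, day 60 and day 120 spirometry would exist. This stands to the extent that the loss is not certain and progression need not be added to the 7.1 list. It does not settle the matter. Those sections speak of leaving the treatment part, whereas 5.1 speaks of removal from the study. Section 7.1 preserves data acquired before termination, which would contain no post-dose lung function.

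A second reply is that replacing a patient does not exclude her data, and that the sentence, coming straight after DLT evaluability, probably just fills the DLT count. That is a fair reading of the intent. The sentence that follows it, the 90%-dose rule, is what takes her out of response evaluation, so deleting the replacement rule alone would not bring her back.

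A reader might infer that the lung-safety signal is hidden altogether. The documents do not support this. Everyone with one dose is in the safety set (sections 5.1, 9.2, 11.2), section 9.3 records worsening of the disease under study as an adverse event, and section 9.2 promises a summary for each patient with special attention to lung-function changes. A reader might also infer that worsening within 5 weeks must be drug harm. Section 1.1 describes LAM in general, not patients on a stable rapalog, and no short-term rate is given, so such worsening calls for examination and proves nothing by itself.

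**Conclusion.** The point holds as a conflict within the protocol. Followed as written, section 5.1 allows patients who progress before 5 weeks to be replaced and makes them non-evaluable for response, and the schedule gives them no lung-function test after day 0. The intention-to-treat statements point the other way but do not say what happens after removal from the study.

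The resulting bias favours simvastatin and concerns descriptive secondary outcomes: response, FEV1, FVC, DLCO and clinical benefit. The primary safety data keep these patients, and day 30 VEGF-D and questionnaires may partly represent them. The selection acts only on the first 5 weeks; the protocol has no rule to replace a patient who worsens later. The size cannot be estimated from the documents, and the working figures rest on assumed numbers of replacements and assumed FEV1 losses.

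**What to change.** - **Section 5.1:** state that replacement fills only the DLT-evaluable count and that the replaced patient stays in every other summary.
- **Secondary summaries:** report response, lung function and clinical benefit in all patients with at least one dose, showing how many lack a post-dose value. Keep the 90%-dose set as supplementary only.
- **Clinical benefit:** define it together with clinical progression, and count a patient removed for progression as not showing benefit.
- **Sections 6.1 and 10.12:** extend the continued-assessment text to patients removed for progression.
- **Final visit in 7.1 and exit visit in 10.12:** include spirometry with DLCO, VEGF-D, SGRQ and FPI, all of which are already in the Visit 6 schedule.
- **Reporting:** give the number replaced and the reasons.

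Naming progression in the 7.1 list is optional. The cost is amendment wording, slightly less favourable figures if early progression occurs, and Visit 6 assessments brought forward for a patient who leaves early. No new type of procedure is needed.
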